8.3 Pharmacodynamic Biomarker Assessments

Blood samples for PD biomarker analysis and verdiperstat-specific PD analysis should be collected at Baseline and Weeks 4, 8, 16, and 24 in the Treatment Phase, and at Weeks 16, 28 and 52 for participants who are in the OLE. Participants who discontinue early from study medication are not required to have PD samples collected at the early discontinuation visit.

PD biomarkers should be collected along with the PK samples, so that one pre-dose PD sample is collected at each specified visit. For each sample, the time of the last dose of study drug prior to sample collection and time of the PD sample collection should be reported on the CRF. The verdiperstat-specific PD biomarkers that will be analyzed are MPO protein and MPO activity. Uric Acid will be collected and results remain blinded throughout the duration of the trial

9 SAFETY AND ADVERSE EVENTS

9.1 Adverse Events of Special Interest – Thyroid Function

Reversible changes in thyroid function tests were observed during the preclinical studies and clinical studies with verdiperstat. Based on prior trials, a small percentage of participants may be expected to develop mild (subclinical) hypothyroidism generally with serum TSH < 10 mIU/L. Laboratory monitoring of thyroid function will be performed and documented throughout this study. Site Investigators should review TSH levels and note the trend over time. The Central Laboratory will flag any TSH \geq ULN, and T3 and free T4 analysis should be performed.

Any significant abnormal findings should be discussed with the study Medical Monitor and may be followed up as per local practice (e.g., investigations and consultation with endocrinologist). In cases of suspected hypothyroidism, repeat thyroid function tests should be measured and levothyroxine replacement therapy should be considered. Initiation of treatment is at the discretion of the SI.

Potential initiation of levothyroxine (T4) replacement therapy may be considered according to the following guidelines:

- For a serum TSH between 5 and 10, levothyroxine 0.05 mg daily (50 mcg) is a reasonable dose to prescribe.
- For a serum TSH between 10 and 20, levothyroxine 0.075 mg daily (75 mcg) is a reasonable dose to prescribe.
- For a serum TSH greater than 20, many physicians would feel more comfortable having an endocrinologist treat such participants.

If signs/symptoms of hypothyroidism (i.e. adverse event, initiation of levothyroxine) and/or significant changes in thyroid function develop, collection of follow up clinical chemistry samples and/or unscheduled study visits may be warranted. It is recommended to wait for 5 or 6 half-lives (5 – 6 weeks) to retest thyroid function. Serum T3, free T4 and TSH should be monitored in such participants, and the serum TSH assesses whether therapy is adequate.

If there are clinically significant issues with tolerability that are not able to be treated adequately with levothyroxine replacement therapy, the SI may consider modifications to the dosage regimen. Consultation with the Medical Monitor is required. Modifications may include reducing the dose of verdiperstat /matching placebo to 300 mg BID or taking a dose holiday. Any such modifications to the dosage regimen should be noted in the CRF.

10 REGIMEN-SPECIFIC STATISTICAL CONSIDERATIONS

10.1 Deviations from the Default Master Protocol Trial Design

The statistical design for this regimen will be in accordance with the default statistical design described in Appendix I of the master protocol with only one deviation. This regimen will not include interim analyses for early success. As such, unless this regimen is stopped early for futility, it will enroll to the maximum sample size. At the final analysis, the treatment will be considered success relative to the shared control group if the posterior probability of superiority is greater than 98.0%. This value was selected by simulation to control the overall one-sided Type I error rate across the null scenarios to less than 2.5%. Results are based on 5000 simulations per scenario.

10.2 Regimen Specific Operating Characteristics

Clinical trial simulation is used to quantify operating characteristics for this regimen given the difference from the default design. The simulation of virtual participants and the simulation scenarios are as described in Appendix I to the master protocol. We present here the operating characteristics for the regimen, according to the default design but with no opportunity to stop early for success. Futility is considered non-binding and as such, Table 10.2.1 shows null hypothesis scenarios and resulting Type I error with no futility stopping. We show null and alternative hypothesis scenarios inclusive of futility stopping in Tables 10.2.2 and 10.2.3. Table 10.2.2 shows operating characteristics under the base case assumptions and Table 10.2.3 shows operating characteristics for the various sensitivity scenarios.

This regimen will be one of the first three regimens to be enrolled in the platform and so there are no participants in the shared control from regimens already complete. The comparison to control will rely entirely upon concurrently randomized controls. Concurrently randomized controls will be defined according to Appendix I to the master protocol.

| Table 10.2.1: Null Hypothesis Scenarios with No Early Futility Stopping | | | | | | |
|--|-------------------------------|---------------|----------------------------|----------------------------|-----------------------------|-----------------|
| Sensitivity Scenario | Mean Duration (Months) | Mean N | Prob. Early Success | Prob. Total Success | Prob. Early Futility | Mean DRR |
| Null Treatment Effect (0% Slowing; Mort HR = 1.0) | | | | | | |
| Base | 15 | 160 | 0.000 | 0.020 | 0.000 | 1.007 |
| Slower Accrual | 27 | 160 | 0.000 | 0.023 | 0.000 | 1.007 |
| Faster Accrual | 11 | 160 | 0.000 | 0.023 | 0.000 | 1.008 |
| Less Dropout | 15 | 160 | 0.000 | 0.021 | 0.000 | 1.006 |
| More Dropout | 15 | 160 | 0.000 | 0.023 | 0.000 | 1.007 |
| Reg. Start Same Time | 18 | 160 | 0.000 | 0.025 | 0.000 | 1.005 |

| Table 10.2.1: Null Hypothesis Scenarios with No Early Futility Stopping | | | | | | |
|--|-------------------------------|---------------|----------------------------|----------------------------|-----------------------------|-----------------|
| Sensitivity Scenario | Mean Duration (Months) | Mean N | Prob. Early Success | Prob. Total Success | Prob. Early Futility | Mean DRR |
| Reg. Start 3 Months Apart | 11 | 160 | 0.000 | 0.025 | 0.000 | 1.017 |
| ALSFRS-R Slower Less Var. Progress | 15 | 160 | 0.000 | 0.022 | 0.000 | 1.006 |
| ALSFRS-R Faster More Var. Progress | 15 | 160 | 0.000 | 0.022 | 0.000 | 1.007 |
| ALSFRS-R Lower Resid. Error | 15 | 160 | 0.000 | 0.024 | 0.000 | 1.006 |
| ALSFRS-R Higher Resid. Error | 15 | 160 | 0.000 | 0.022 | 0.000 | 1.007 |
| 10% Mortality Rate | 15 | 160 | 0.000 | 0.025 | 0.000 | 1.005 |
| 20% Mortality Rate | 15 | 160 | 0.000 | 0.023 | 0.000 | 1.006 |

| Table 10.2.2: Base Scenarios Operating Characteristics. Null and Alternative Hypotheses With Futility Stopping | | | | | | | |
|---|-----------------|--------------------------------|---------------|----------------------------|----------------------------|-----------------------------|-----------------|
| Scenario (% Slowing ALSFRS-R) | HR Mort. | Mean Duration (Months) | Mean N | Prob. Early Success | Prob. Total Success | Prob. Early Futility | Mean DRR |
| 0% | 1 | 14 | 155 | 0.000 | 0.020 | 0.290 | 1.049 |
| 25% | .75 | 15 | 160 | 0.000 | 0.615 | 0.008 | 0.747 |
| 30% | .7 | 15 | 160 | 0.000 | 0.776 | 0.002 | 0.694 |
| 35% | .65 | 15 | 160 | 0.000 | 0.888 | 0.001 | 0.642 |
| 30% | 1 | 15 | 160 | 0.000 | 0.731 | 0.003 | 0.708 |
| 30% | 1.3 | 15 | 160 | 0.000 | 0.683 | 0.004 | 0.722 |

| Table 10.2.3: Base and Sensitivity Scenarios with Early Futility Stopping. | | | | | | |
|---|-------------------------------|---------------|----------------------------|----------------------------|-----------------------------|-----------------|
| Sensitivity Scenario | Mean Duration (Months) | Mean N | Prob. Early Success | Prob. Total Success | Prob. Early Futility | Mean DRR |
| Null Treatment Effect (0% Slowing; Mort HR = 1.0) | | | | | | |
| Base | 14 | 155 | 0.000 | 0.020 | 0.290 | 1.049 |
| Slower Accrual | 23 | 143 | 0.000 | 0.023 | 0.347 | 1.063 |
| Faster Accrual | 11 | 160 | 0.000 | 0.023 | 0.257 | 1.034 |
| Less Dropout | 14 | 155 | 0.000 | 0.021 | 0.280 | 1.047 |
| More Dropout | 14 | 155 | 0.000 | 0.023 | 0.271 | 1.047 |
| Reg. Start Same Time | 16 | 154 | 0.000 | 0.025 | 0.281 | 1.035 |
| Reg. Start 3 Months Apart | 10 | 160 | 0.000 | 0.025 | 0.219 | 1.043 |
| ALSFRS-R Slower Less Var. Progress | 14 | 155 | 0.000 | 0.022 | 0.283 | 1.049 |
| ALSFRS-R Faster More Var. Progress | 14 | 155 | 0.000 | 0.022 | 0.300 | 1.047 |
| ALSFRS-R Lower Resid. Error | 14 | 155 | 0.000 | 0.024 | 0.295 | 1.046 |
| ALSFRS-R Higher Resid. Error | 14 | 155 | 0.000 | 0.022 | 0.284 | 1.050 |
| 10% Mortality Rate | 14 | 155 | 0.000 | 0.025 | 0.286 | 1.046 |
| 20% Mortality Rate | 14 | 155 | 0.000 | 0.023 | 0.294 | 1.046 |
| Alternative Common Treatment Effect (30% Slowing; Mort HR = .70) | | | | | | |
| Base | 15 | 160 | 0.000 | 0.776 | 0.002 | 0.694 |
| Slower Accrual | 27 | 160 | 0.000 | 0.771 | 0.005 | 0.695 |
| Faster Accrual | 11 | 160 | 0.000 | 0.762 | 0.002 | 0.694 |
| Less Dropout | 15 | 160 | 0.000 | 0.745 | 0.003 | 0.694 |
| More Dropout | 15 | 160 | 0.000 | 0.722 | 0.003 | 0.694 |
| Reg. Start Same Time | 18 | 160 | 0.000 | 0.782 | 0.002 | 0.691 |

HEALEY ALS Platform Trial
Regimen-Specific Appendix B, Verdiperstat
Version 6.0 , 02-December-2021
CONFIDENTIAL

| Table 10.2.3: Base and Sensitivity Scenarios with Early Futility Stopping. | | | | | | |
|--|-------------------------------|---------------|----------------------------|----------------------------|-----------------------------|-----------------|
| Sensitivity Scenario | Mean Duration (Months) | Mean N | Prob. Early Success | Prob. Total Success | Prob. Early Futility | Mean DRR |
| Reg. Start 3 Months Apart | 11 | 160 | 0.000 | 0.681 | 0.003 | 0.700 |
| ALSFRS-R Slower Progress | 15 | 160 | 0.000 | 0.754 | 0.003 | 0.693 |
| ALSFRS-R Faster Progress | 15 | 160 | 0.000 | 0.791 | 0.002 | 0.694 |
| ALSFRS-R Lower Resid. Error | 15 | 160 | 0.000 | 0.793 | 0.003 | 0.692 |
| ALSFRS-R Higher Resid. Error | 15 | 160 | 0.000 | 0.758 | 0.003 | 0.694 |
| 10% Mortality Rate | 15 | 160 | 0.000 | 0.782 | 0.003 | 0.693 |
| 20% Mortality Rate | 15 | 160 | 0.000 | 0.799 | 0.003 | 0.695 |
| Alternative Treatment Effect No Mort. Benefit (30% Slowing; Mort HR = 1.0) | | | | | | |
| Base (5% Mort. Rate) | 15 | 160 | 0.000 | 0.731 | 0.003 | 0.708 |
| 10% Mort. Rate | 15 | 160 | 0.000 | 0.695 | 0.004 | 0.721 |
| 20% Mort. Rate | 15 | 160 | 0.000 | 0.602 | 0.007 | 0.749 |
| Alternative Treatment Effect Worse Mort. (30% Slowing; Mort HR = 1.3) | | | | | | |
| Base (5% Mort. Rate) | 15 | 160 | 0.000 | 0.683 | 0.004 | 0.722 |
| 10% Mort. Rate | 15 | 160 | 0.000 | 0.592 | 0.008 | 0.750 |
| 20% Mort. Rate | 15 | 160 | 0.000 | 0.411 | 0.015 | 0.803 |

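### Table 10.2.3 gives lower power with both less and more dropout than at Base, so at least one of the three rows is wrong or misdescribed

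*Protocol*

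**What the plan says.** Protocol Section 10.2, Table 10.2.3, reports simulated operating characteristics with futility stopping. Its columns are mean duration, mean N, probability of early success, probability of total success (the power), probability of early futility and mean disease rate ratio (DRR). In the block for 30% slowing and a mortality hazard ratio of 0.70, three rows matter:

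- "Base | 15 | 160 | 0.000 | 0.776 | 0.002 | 0.694"
- "Less Dropout | 15 | 160 | 0.000 | 0.745 | 0.003 | 0.694"
- "More Dropout | 15 | 160 | 0.000 | 0.722 | 0.003 | 0.694"

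Table 10.2.2 gives the same Base result: "30% | .7 | 15 | 160 | 0.000 | 0.776 | 0.002 | 0.694".

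Section 10.1 states that the results rest on 5000 simulations per scenario. For the scenario definitions, Section 10.2 refers to Appendix I of the master protocol, which was not among the documents reviewed. The protocol gives no dropout rate for any of the three rows and does not comment on their order.

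**The concern.** Dropout removes follow-up, and follow-up carries the information on the rate of decline. With everything else held fixed, power should fall as dropout rises, so Base should sit between Less Dropout and More Dropout. The printed order is Base, then Less Dropout, then More Dropout. Read literally, both less and more dropout cost power, which is not credible.

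The 77.6% is the protocol's stated power for this effect, and these two rows are its only check against another dropout rate. As printed, a reader cannot tell how much power is gained or lost relative to the Base dropout rate, or whether 77.6% is itself right. Section 4.2.2 says that all participants have been enrolled, so what is at stake is correct reporting of the design's power, not the sample size.

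**Working it through.** **Inputs.** Power of 0.776, 0.745 and 0.722 from Table 10.2.3; 5000 simulations per scenario from Section 10.1. Runs are treated as independent. Common random seeds with positive correlation between runs would make the standard errors smaller and the evidence stronger.

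**1. Is the Base figure consistent with its neighbours?** Take power = Φ((1 − DRR)/SE − z), with z = 2.054 for the 98.0% threshold, and obtain SE from the other common-effect rows of Table 10.2.2.

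- 25% slowing (DRR 0.747, power 0.615): SE = 0.253/(2.054 + 0.292) = 0.1078.
- 35% slowing (DRR 0.642, power 0.888): SE = 0.358/(2.054 + 1.216) = 0.1095.
- Mean SE 0.1087. At DRR 0.694 the predicted power is Φ(0.306/0.1087 − 2.054) = 0.777, against 0.776 printed.

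So 0.776 is unlikely to be a typing slip. This does not test the dropout rate behind it, because the neighbouring rows presumably share that rate. The dropout rows cannot be reproduced without their dropout rates.

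**2. Is the order simulation error?** For two rows, SE = √[p₁(1 − p₁)/5000 + p₂(1 − p₂)/5000].

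| Comparison | Difference | SE | z | 95% interval |
|---|---|---|---|---|
| Base − Less | 0.031 | 0.0085 | 3.63 | 0.014 to 0.048 |
| Base − More | 0.054 | 0.0087 | 6.24 | 0.037 to 0.071 |
| Less − More | 0.023 | 0.0088 | 2.60 | 0.006 to 0.040 |

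For Base − Less, SE = √(0.776 × 0.224/5000 + 0.745 × 0.255/5000) = 0.00853, so z = 0.031/0.00853 = 3.63 and two-sided p = 0.00028.

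- Worst-case rounding (0.7755 against 0.7455) gives z = 3.52.
- Bonferroni over the 12 non-Base rows in the block gives 12 × 0.00028 = 0.0034.

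Less Dropout above More Dropout is the expected order. The anomaly is where Base lies.

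**3. Do the other columns explain it?**

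- *Futility:* 0.002 against 0.003. Allowing for rounding, the gap is at most 0.0035 − 0.0015 = 0.002. Removing that leaves 0.029/0.00853, or z = 3.4.
- *Size and effect:* N (160), duration (15 months) and mean DRR (0.694) are identical.
- *Effective threshold:* null success is 0.020, 0.021 and 0.023 (Table 10.2.1), which is within simulation error (Base against Less z = 0.35, Base against More z = 1.03).
- *Exchanged labels:* Base would still lie above both rows.

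**4. Do other paired scenarios behave?** Base lies between the two values for progression (0.754, 0.791), residual error (0.758, 0.793) and regimen start (0.681, 0.782). Both accrual rows are below Base, slower at 0.771 and faster at 0.762 ("Faster Accrual | 11 | 160 | 0.000 | 0.762 | 0.002 | 0.694"), but within simulation error (z = 0.60 and 1.66). Dropout is the only pair that Base falls outside by more than noise.

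**5. Do the null rows locate the fault?** Null futility has the same order: 0.290 ("Base | 14 | 155 | 0.000 | 0.020 | 0.290 | 1.049"), 0.280 ("Less Dropout | 14 | 155 | 0.000 | 0.021 | 0.280 | 1.047") and 0.271 ("More Dropout | 14 | 155 | 0.000 | 0.023 | 0.271 | 1.047"). Base against Less there has z = 1.11, so it does not help.

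**6. How far should dropout move power?** As an illustration only, take a random-slopes model with ignorable dropout, calibrated to 0.776 at an assumed 10% dropout, with assumed slope SD 0.5 to 1.1 and residual SD 1 to 2.5. Power is then 0.784 to 0.792 at 5% dropout, 0.792 to 0.806 at none, and 0.741 to 0.758 at 20%. It falls as dropout rises throughout. The printed 0.745 would mean that Less Dropout carries about 7% less information than Base.

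**The case against.** The strongest reply is that short row labels do not prove that only dropout was varied. The definitions are in Appendix I, and the same table does shorten its labels: the progression rows in the null block mention variability as well as speed, while the matching rows in the 30% slowing block mention only speed. If Appendix I shows another difference, the simulations could be sound. That possibility stands, and it is why the conclusion says wrong or misdescribed. In that case, a row labelled by dropout alone does not tell the reader what was changed, and the label needs correcting.

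Second, the test depends on the run count. At 1000 runs z would be only 1.63. The 5000 figure appears in Section 10.1, next to the choice of threshold, and is not repeated in Section 10.2. Its natural reading covers all the tables, and nothing in the documents suggests a smaller count for the power scenarios.

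Third, agreement with Table 10.2.2 and the neighbouring effect sizes may point to the dropout rows, above all Less Dropout, as the likelier fault. That is a fair inference against an isolated slip in Base, but it is not proof, for the reason given in step 1.

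Fourth, the practical effect is limited: no decision rule uses these rows, and the regimen-start scenario moves power further (to 0.681). This bears on how much the point matters, not on whether the rows agree.

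**Conclusion.** The point holds. The three rows cannot all be right as labelled. Base exceeds Less Dropout by 0.031 (95% interval 0.014 to 0.048), beyond simulation error at 5000 runs.

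The documents do not identify the faulty row, so the size of the error is conditional:

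- If the dropout rows are right, Base would be expected between about 0.722 and 0.745, and 0.776 is too high by 0.776 − 0.745 = 0.031 to 0.776 − 0.722 = 0.054.
- If Base is right, Less Dropout would be expected at or above 0.776. More Dropout cannot be sized without the dropout rates.

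Both readings carry simulation error (SE of a difference about 0.009). The conclusion assumes that the 5000 runs apply to these rows and that the labels mean only dropout differs; if the second assumption fails, the fault lies in the description. The null success rates give no sign of a Type I error problem.

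**What to change.** Check the Base, Less Dropout and More Dropout rows against the simulation output and the Appendix I settings. Re-run any row that does not match, varying only the dropout rate from Base. State the dropout rate for each of the three scenarios, and correct whichever value or label is wrong.

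- If Base is in error, restate the 77.6% in Tables 10.2.2 and 10.2.3 and recheck the other rows that use the Base dropout rate, including the null rows in Table 10.2.1.
- If the dropout rows are in error, correct them, and the matching null rows if they are affected.
- If another setting also differs, say so in the label.

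The first step costs a look at three rows of existing output and one sentence giving the dropout rates. The cost is larger only if Base proves wrong, because more rows then need the same check. No change to the sample size, the 98.0% threshold or the analysis is needed.

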10.3 Sharing of Controls from Other Regimens

The primary analysis of this regimen will include sharing of all controls from the other regimens. This is justified by the minor differences in inclusion/exclusion criteria of the RSA, such that there are no expected systematic differences in the primary endpoint between the controls across regimens.

Appendix I: The Bulbar Function Scale (CNS-BFS)

| BULBAR FUNCTION SCALE (CNS-BFS) | | | | | | |
|--|---------------------------|---------------------------|---------------------------------|--------------------------------------|-------------------------------------|--|
| SIALORRHEA | Does Not Apply (1) | Applies Rarely (2) | Applies Occasionally (3) | Applies Frequently (4) | Applies Most of the Time (5) | |
| 1. Excessive saliva is a concern to me. |  |  |  |  |  | |
| 2. I take medication to control drooling. |  |  |  |  |  | |
| 3. Saliva causes me to gag or choke. |  |  |  |  |  | |
| 4. Drooling causes me to be frustrated or embarrassed. |  |  |  |  |  | |
| 5. In the morning I notice saliva on my pillow. |  |  |  |  |  | |
| 6. My mouth needs to be dabbed to prevent drooling. |  |  |  |  |  | |
| 7. My secretions are not manageable. |  |  |  |  |  | |
| | | | | TOTAL Sialorrhea Score: _____ | | |
| SPEECH | Does Not Apply (1) | Applies Rarely (2) | Applies Occasionally (3) | Applies Frequently (4) | Applies Most of the Time (5) | Unable to Communicate by Speaking (6) |
| 1. My speech is difficult to understand. |  |  |  |  |  |  |

| | | | | | | |
|--|---------------------------|---------------------------|---------------------------------|----------------------------------|-------------------------------------|-----------------------|
| 2. To be understood I repeat myself. |  |  |  |  |  |  |
| 3. People who understand me tell other people what I said. |  |  |  |  |  |  |
| 4. To communicate I write things down or use devices such as a computer. |  |  |  |  |  |  |
| 5. I am talking less because it takes so much effort to speak. |  |  |  |  |  |  |
| 6. My speech is slower than usual. |  |  |  |  |  |  |
| 7. It is hard for people to hear me. |  |  |  |  |  |  |
| | | | | TOTAL Speech Score: _____ | | |
| SWALLOWING | Does Not Apply (1) | Applies Rarely (2) | Applies Occasionally (3) | Applies Frequently (4) | Applies Most of the Time (5) | |
|  Feeding tube is in place | | | | | | |
| 1. Swallowing is a problem. |  |  |  |  |  | |
| 2. Cutting my food makes it easier to chew and swallow. |  |  |  |  |  | |
| 3. To get food down I have switched to a soft diet. |  |  |  |  |  | |
| 4. After swallowing I gag or choke. |  |  |  |  |  | |

| | | | | | | |
|--|-----------------------|-----------------------|-----------------------|--------------------------------------|-----------------------|--|
| 5. It takes longer to eat. |  |  |  |  |  | |
| 6. My weight is dropping because I can't eat normally. |  |  |  |  |  | |
| 7. Food gets stuck in my throat. |  |  |  |  |  | |
| | | | | TOTAL Swallowing Score: _____ | | |
| | | | | OVERALL SCORE: _____ | | |

Appendix II: The ALSAQ-40

ALSAQ-40

Please complete this questionnaire as soon as possible. If you have any difficulties filling in this questionnaire by yourself, please have someone help you. However it is **your** responses that we are interested in.

The questionnaire consists of a number of statements about difficulties that you may have experienced **during the last 2 weeks**. There are no right or wrong answers: your first response is likely to be the most accurate for you. **Please check the box that best describes your own experiences or feelings.**

Please answer every question even though some may seem very similar to others, or may not seem relevant to you.

All the information you provide is **confidential**.

The following statements all refer to difficulties that you may have had **during the last 2 weeks**. Please indicate, by checking the appropriate box, how often the following statements have been true for you.

ALSAQ-40 © Oxford University Innovation Limited, 2000. All rights reserved. Translated from English (UK) to English (USA) by Oxford Outcomes Ltd.

The following statements all refer to certain difficulties that you may have had during the last 2 weeks. Please indicate, by checking the appropriate box, how often the following statements have been true for you.

If you cannot walk at all
please check **Always/cannot walk at all**.

How often during the last 2 weeks have the following been true?

Please check one box for each question.

| | Never | Rarely | Some- times | Often | Always or cannot walk at all |
|--|--------------------------|--------------------------|--------------------------|--------------------------|--|
| 1. I have found it difficult to walk short distances, e.g. around the house. |  |  |  |  |  |
| 2. I have fallen over while walking. |  |  |  |  |  |
| 3. I have stumbled or tripped while walking. |  |  |  |  |  |
| 4. I have lost my balance while walking. |  |  |  |  |  |
| 5. I have had to concentrate while walking. |  |  |  |  |  |

Please make sure that you have checked one box for each question before going on to the next page.

ALSAQ-40 © Oxford University Innovation Limited, 2000. All rights reserved. Translated from English (UK) to English (USA) by Oxford Outcomes Ltd.

The following statements all refer to certain difficulties that you may have had during the last 2 weeks. Please indicate, by checking the appropriate box, how often the following statements have been true for you.

*If you are not able to perform the activity at all please check **Always/cannot at all***

How often during the last 2 weeks have the following been true?

Please check one box for each question

| | Never | Rarely | Some-times | Often | Always or cannot do at all |
|--|--------------------------|--------------------------|--------------------------|--------------------------|----------------------------|
| 6. Walking had worn me out. |  |  |  |  |  |
| 7. I have had pains in my legs while walking. |  |  |  |  |  |
| 8. I have found it difficult to go up and down the stairs. |  |  |  |  |  |
| 9. I have found it difficult to stand up. |  |  |  |  |  |
| 10. I have found it difficult to move from sitting in a chair to standing upright. |  |  |  |  |  |

Please make sure that you have checked one box for each question before going on to the next page.

ALSAQ-40 © Oxford University Innovation Limited, 2000. All rights reserved. Translated from English (UK) to English (USA) by Oxford Outcomes Ltd.

The following statements all refer to certain difficulties that you may have had during the last 2 weeks. Please indicate, by checking the appropriate box, how often the following statements have been true for you.

*If you cannot do the activity at all
please check **Always/cannot do at all**.*

***How often during the last 2 weeks
have the following been true?***

Please check one box for each question

| | Never | Rarely | Some- times | Often | Always or cannot do at all |
|--|--------------------------|--------------------------|--------------------------|--------------------------|-------------------------------------|
| 11. I have had difficulty using my arms and hands. |  |  |  |  |  |
| 12. I have found turning and moving in bed difficult. |  |  |  |  |  |
| 13. I have had difficulty picking things up. |  |  |  |  |  |
| 14. I have had difficulty holding books or newspapers, or turning pages. |  |  |  |  |  |
| 15. I have had difficulty writing clearly. |  |  |  |  |  |

*Please make sure that you have checked one box for each question
before going on to the next page.*

ALSAQ-40 © Oxford University Innovation Limited, 2000. All rights reserved. Translated from English (UK) to English (USA) by Oxford Outcomes Ltd.

The following statements all refer to certain difficulties that you may have had during the last 2 weeks. Please indicate, by checking the appropriate box, how often the following statements have been true for you.

*If you cannot do the activity at all please check **Always/cannot do at all**.*

How often during the last 2 weeks have the following been true?

Please check one box for each question

| | Never | Rarely | Some-times | Often | Always or cannot do at all |
|---|--------------------------|--------------------------|--------------------------|--------------------------|----------------------------|
| 16. I have found it difficult to do jobs around the house. |  |  |  |  |  |
| 17. I have found it difficult to feed myself. |  |  |  |  |  |
| 18. I have had difficulty combing my hair or brushing and/or flossing my teeth. |  |  |  |  |  |
| 19. I have had difficulty getting dressed. |  |  |  |  |  |
| 20. I have had difficulty washing at the bathroom sink. |  |  |  |  |  |

Please make sure that you have checked one box for each question before going on to the next page.

ALSAQ-40 © Oxford University Innovation Limited, 2000. All rights reserved. Translated from English (UK) to English (USA) by Oxford Outcomes Ltd.

The following statements all refer to certain difficulties that you may have had during the last 2 weeks. Please indicate, by checking the appropriate box, how often the following statements have been true for you.

*If you cannot do the activity at all please check **Always/cannot do at all**.*

How often during the last 2 weeks have the following been true?

Please check one box for each question

| | Never | Rarely | Sometimes | Often | Always or cannot do at all |
|---|--------------------------|--------------------------|--------------------------|--------------------------|----------------------------|
| 21. I have had difficulty swallowing. |  |  |  |  |  |
| 22. I have had difficulty eating solid food. |  |  |  |  |  |
| 23. I have had difficulty drinking liquids. |  |  |  |  |  |
| 24. I have had difficulty participating in conversations. |  |  |  |  |  |
| 25. I have felt that my speech has not been easy to understand. |  |  |  |  |  |

Please make sure that you have checked one box for each question before going on to the next page.

ALSAQ-40 © Oxford University Innovation Limited, 2000. All rights reserved. Translated from English (UK) to English (USA) by Oxford Outcomes Ltd.

The following statements all refer to certain difficulties that you may have had during the last 2 weeks. Please indicate, by checking the appropriate box, how often the following statements have been true for you.

*If you cannot do the activity at all
please check **Always/cannot do at all**.*

***How often during the last 2 weeks
have the following been true?***

Please check one box for each question

| | Never | Rarely | Some- times | Often | Always or cannot do at all |
|---|--------------------------|--------------------------|--------------------------|--------------------------|--|
| 26. I have stuttered or slurred my speech. |  |  |  |  |  |
| 27. I have had to talk very slowly. |  |  |  |  |  |
| 28. I have talked less than I used to do. |  |  |  |  |  |
| 29. I have been frustrated with my speech. |  |  |  |  |  |
| 30. I have felt self-conscious about my speech. |  |  |  |  |  |

*Please make sure that you have checked **one box for each question**
before going on to the next page.*

ALSAQ-40 © Oxford University Innovation Limited, 2000. All rights reserved. Translated from English (UK) to English (USA) by Oxford Outcomes Ltd.

The following statements all refer to certain difficulties that you may have had during the last 2 weeks. Please indicate, by checking the appropriate box, how often the following statements have been true for you.

How often during the last 2 weeks have the following been true?

Please check one box for each question

| | Never | Rarely | Some-times | Often | Always |
|--|--------------------------|--------------------------|--------------------------|--------------------------|--------------------------|
| 31. I have felt lonely. |  |  |  |  |  |
| 32. I have been bored. |  |  |  |  |  |
| 33. I have felt embarrassed in social situations. |  |  |  |  |  |
| 34. I have felt hopeless about the future. |  |  |  |  |  |
| 35. I have worried that I am a burden to other people. |  |  |  |  |  |

Please make sure that you have checked one box for each question before going on to the next page.

ALSAQ-40 © Oxford University Innovation Limited, 2000. All rights reserved. Translated from English (UK) to English (USA) by Oxford Outcomes Ltd.

The following statements all refer to certain difficulties that you may have had during the last 2 weeks. Please indicate, by checking the appropriate box, how often the following statements have been true for you.

How often during the last 2 weeks have the following been true?

Please check one box for each question

| | Never | Rarely | Sometimes | Often | Always |
|--|--------------------------|--------------------------|--------------------------|--------------------------|--------------------------|
| 36. I have wondered why I keep going. |  |  |  |  |  |
| 37. I have felt angry because of the disease. |  |  |  |  |  |
| 38. I have felt depressed. |  |  |  |  |  |
| 39. I have worried about how the disease will affect me in the future. |  |  |  |  |  |
| 40. I have felt as if I have lost my independence |  |  |  |  |  |

Please make sure that you have checked one box for each question.

Thank you for completing this questionnaire.

ALSAQ-40 © Oxford University Innovation Limited, 2000. All rights reserved. Translated from English (UK) to English (USA) by Oxford Outcomes Ltd.
